Only one measurement per subject will be taken on the left cheek, near to the side of the nose (if it will be possible on a nonlesional skin). The value will be reported in the CRF.

Sebumetry measurement

Corneometry measurements

Phmetry measurement

- *Confocal microscopy analysis (only for CHU Nantes; n≈ 30) (5)*

From the beginning of the inclusions and until the number of subjects will be reached (n≈ 30), the investigator will propose a complementary examination that the subjects will be free to refuse.

At W0 (before any application) and W12 (after a 12-week application period), instrumental measurements will be performed by investigator at CHU Nantes.

a) Acquisitions:

RCM Vivascope® (1500/3000) is a confocal laser scanning microscope for *in vivo* use, with an imaging wavelength of 830 nm, used to acquire standardized pictures of the skin. Confocal images are obtained by analyzing the reflection of a diode laser in the skin. Resolution allows analyzing the epidermis and upper layers of the stratum reticulare, up to a depth of 200 µm with a lateral resolution <1.25 µm. The lens will be directly applied onto the selected skin area (on 3 nonlesional skin area: forehead, right temple and right mandibular). Crodamol oil will be used as a conductive interface between the skin and the lens. Each image corresponded to a 500 µm x 500 µm horizontal section. A Vivacube® of 3 mm x 3 mm is a mosaic of 36 images, on three horizontal section levels.

b) Analysis:

Confocal images will be analyzed by two confocal microscopy experts ([name], [name]).

The assessments features will be:

- Total number of hair follicles per cube at a mean depth of 38 µm
- Diameter of the infundibulum
- Aspect of the border (thickness)
- Onion-like appearance
- Presence of amorphous material into the infundibulum
- Signs of inflammation
- Vascularization
- Presence of *Demodex* mites

- Efficacy questionnaire

Subjects will complete an efficacy questionnaire at the last visit (after a 12-week application period of the IP (cosmetic product & drug)).

The following items will be evaluated by the subjects:

| | ITEMS |
|----|---|
| 1 | Les imperfections sont moins visibles Imperfections are less visible |
| 2 | La peau est assainie/purifiée The skin is cleansed/purified |
| 3 | Le teint est homogène/uniforme The complexion is homogeneous / uniform |
| 4 | La peau est confortable The skin is comfortable |

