| 5 | La peau est comme hydratée The skin is like hydrated |
| 6 | La peau est plus lisse The skin is smoother |
| 7 | La peau est plus douce The skin is softer |
| 8 | La peau est plus souple The skin is suppler |
| 9 | La peau est moins brillante The skin is less brilliant |
| 10 | La peau est matifiée The skin is matified |
| 11 | L'excès de sébum est réduit Excess sebum is reduced |
| 12 | La peau a un toucher mat The skin has a matte touch |
| 13 | Les pores de la peau sont resserrés The pores of the skin are tightened |
| 14 | Les rougeurs de la peau sont atténuées Redness of the skin are reduced |
| 15 | Le grain de peau est affiné The skin texture is refined |
| 16 | Les marques de la peau sont moins visibles The marks of the skin are less visible |

The following scale will be used:

- Agree (“D'accord”)
- Somewhat agree (“Plutôt d'accord”)
- Neither agree, nor disagree (“Ni d'accord ni pas d'accord”)
- Somewhat disagree (“Plutôt pas d'accord”)
- Disagree (“Pas d'accord”)

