11.6.2.3. Local tolerance

- Clinical assessments

At W0 (before any application), W4 (after a 4-week application period), W8 (after an 8-week application period) and W12 (after a 12-week application period), a clinical assessment of the face skin condition will be performed by the Dermatologist:

- Physical signs: erythema, dryness and scaling
- Functional signs*: tightness, prickling, itching, burning sensation and others

The following scale will be used:

Rating 0: none ("absence")

Rating 1: slight ("léger")

Rating 2: moderate ("modéré")

Rating 3: severe ("sévère")

* During the study, the subjects will have to record any skin discomfort, intensity (slight, moderate or severe) and duration in their daily log. Functional signs will be assessed by the Dermatologist from a review of the daily log and interrogatory of the subject.

- Overall tolerance

In addition, at W12 (after a 12-week application period), the Dermatologist and the subject will state about the overall tolerance of the IP (cosmetic product & drug) based on rating scale:

- Excellent tolerance
- Good tolerance
- Medium tolerance
- Poor tolerance

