14.3. Data description and statistical analysis

Subject disposition

Data from subjects of all defined populations, from subjects who completed the study, and from subjects who withdrew from the study will be summarized by product group using descriptive statistics.

Data from subjects who withdrew from the study will also be summarized by reason for withdrawal using descriptive statistics.

Demographic and Baseline Characteristics

Subjects demographic and baseline characteristics will be summarized by product group using descriptive statistics. For continuous variables, descriptive statistics (n, mean, standard deviation, standard error, median, minimum, and maximum) will be provided. For categorical variables, subject counts and percentages will be provided. Categories for missing data will be presented if necessary.

Efficacy analyses

Analyses will use 2-sided tests at the 5% significance level, except the normality tested at the threshold of 1% (Shapiro-Wilk test).

For all parameters, descriptive statistical tables along with graphics will be performed.

For quantitative parameters (such as clinical counting of cutaneous lesions, sebumetry, corneometry, pHmetry), products will be compared by a covariance analysis with Product and Time as fixed factors, Subject as random factor and value at baseline as covariate (mixed models for repeated longitudinal using SAS® Mixed procedure). The interaction Time x Product will be tested. **Contrasts between products will be evaluated at each time. For the total number of cutaneous lesions, W12 will be considered as the primary contrast.**

Ordinal parameters such as the GEA will be analysed using generalized linear random model for multinomial data (a model for binary data can also be used according to the results of the descriptive analysis), with Subject as random factor, Time and Product as fixed factors and the value at baseline as covariate (SAS® Glimmix Procedure).

All comparisons will be carried out using contrasts. Tests will be followed by a Benjamini-Hochberg adjustment for multiple comparisons.

Data collected [from the efficacy and cosmetic acceptability questionnaires](#) at W12 will be described and compared between products by a chi-square test.

Safety analyses

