Physical and functional signs will be described and analysed using a generalized linear random model for multinomial data (a model for binary data can also be used according to the results of the descriptive analysis), with Subject as random factor, Time and Product as fixed factors (SAS® Glimmix Procedure).

The overall tolerance will be compared between treatments using a chi-square test.

The adverse events will be described and the number of subjects with at least one AE related to the study product will be compared between products by a chi-square test.

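### Overall tolerance at W12 has four ordered levels and a directional aim, but is compared by a chi-square test that ignores the order

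*Combined protocol and SAP*

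**What the plan says.** Section 11.6.2.3 has the dermatologist and the subject each state, at W12, "the overall tolerance of the IP (cosmetic product & drug) based on rating scale" with four levels: excellent, good, medium, poor. Under Safety analyses in section 14.3, "The overall tolerance will be compared between treatments using a chi-square test". No trend, mean-score or stratified version is named. The next sentence uses the same unqualified term for a yes/no outcome: "the number of subjects with at least one AE related to the study product will be compared between products by a chi-square test".

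The questionnaires are treated alike. Under section 11.6.2.2, "Subjects will complete an efficacy questionnaire at the last visit"; it has 16 items on a five-level agree-to-disagree scale with "Neither agree, nor disagree" in the middle. These data, and the 12 cosmetic acceptability items, "at W12 will be described and compared between products by a chi-square test".

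Other graded outcomes get a different treatment: "Ordinal parameters such as the GEA will be analysed using generalized linear random model for multinomial data", and the physical and functional signs have a similar model.

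The aims differ in direction. Section 7.2 sets out to demonstrate improved local tolerance, but only to evaluate skin quality and cosmetic acceptability. For skin quality, a directional aim appears in section 6.

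**The concern.** A Pearson chi-square on a 2 x 4 table gives the same answer if the four categories are shuffled. It asks whether the two distributions differ in any way and spends 3 degrees of freedom doing so. The stated aim is narrower: ratings should move towards the better end. A test that uses the order puts the same information on 1 degree of freedom. The chi-square also returns a p-value with no direction or size.

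What is at stake is limited. Overall tolerance is one supporting rating; the physical and functional signs at four visits carry most of the evidence on tolerance. The rating covers the cosmetic and the drug together, and the drug is common to both arms, so the true shift may be small. In that setting an order-blind test is the more likely to miss a consistent difference.

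**Working it through.** **The plan's own figure.** Section 14.1 gives 90 evaluable per group for the primary endpoint. Two-sample formula times (1 - R²): 2 x (1.960 + 0.842)² x 5.0² / 1.15² = 296.7; 296.7 x (1 - 0.70) = 89.0, given as 90. Then 180 / 0.90 = 200. This reproduces. No rate, effect or power is stated for overall tolerance.

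**Inputs from the protocol.** 90 to 100 per arm at W12 (200 randomised, 10% drop-out, no follow-up after withdrawal, section 9.6). Two centres with 100 randomisation numbers each (section 9.4), randomised 1:1 within centre (section 9.5.1); equal centre sizes are therefore used. Two-sided 5%, stated under Efficacy analyses and assumed to apply here.

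**Assumed inputs.** Control distributions 40/35/18/7, 60/30/8/2 and 25/40/25/10% (excellent to poor), and a proportional-odds shift. No multiplicity adjustment is applied: "Tests will be followed by a Benjamini-Hochberg adjustment for multiple comparisons" stands before the questionnaire and safety paragraphs, so its reach to these tests is unclear.

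**Closed-form check, control 40/35/18/7, odds ratio 2.** Doubling the cumulative odds gives 57.1/28.6/10.7/3.6% in the other arm. With n per arm and category probabilities p and q, Pearson's noncentrality is λ = n Σ (p - q)² / (p + q):

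90 x (0.0302 + 0.0065 + 0.0188 + 0.0107) = 90 x 0.0662 = 5.96.

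The rank test has the same λ, 5.96. Pearson compares it with a 3-df critical value of 7.81, the rank test with a 1-df value of 3.84. Power is 51.5% and 68.5%. The difference comes from the degrees of freedom.

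**Formula and simulation** (40,000 trials per cell; Pearson on pooled counts; tie-corrected van Elteren test, weights 1/(n+1)), 90 per arm:

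| Odds ratio | λ | Pearson, formula | Rank, formula | Pearson, simulated | Van Elteren, simulated |
|---|---|---|---|---|---|
| 1.25 | 0.65 | 9.1% | 12.8% | 9% | 13% |
| 1.5 | 2.12 | 20.2% | 30.7% | 20% | 31% |
| 2 | 5.96 | 51.5% | 68.5% | 51% | 69% |
| 2.5 | 10.0 | 76.3% | 88.6% | 77% | 90% |
| 3 | 13.9 | 89.4% | 96.2% | 91% | 97% |

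**Range.** Over the three control distributions and 90 to 100 per arm, the simulated loss is 3.7-4.5 points at odds ratio 1.25, 10-12 at 1.5, 17-18 at 2 and 3.5-11.5 at 3. A second simulation over six control distributions, from 25/25/25/25 to 60/30/8/2, gave 3.3-4.2 points at 1.25 and 16.3-17.9 at 2.

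**Validity.** Type I error at 5% is 4.1-5.0% for chi-square and 4.8-5.2% for van Elteren. With 60/30/8/2, at least 99% of simulated trials have an expected count below 5 and chi-square is conservative (4.1%).

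**Stratification.** With no centre difference, van Elteren and the unstratified Wilcoxon test agree within 0.2 points. If the centres differ by an assumed odds ratio of 2.25 or 4, stratifying gains 1.5-2.1 or 4.3-6.0 points at treatment odds ratio 2. Most of the benefit therefore comes from using the order.

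**Reverse case.** For control 40/35/18/7 against a polarised 50/20/13/17, λ is 9.16 for Pearson but only 0.08 for the rank test: formula power 72% against 6%. Simulated power over the assumed polarised patterns is 73-85% against 6-7% (four levels) and 56-69% against 6% (five levels).

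**Efficacy items** (five levels; three assumed control distributions). The loss per item at 5% is 5 points at odds ratio 1.25, 13-15 at 1.5, 22-23 at 2 and 5-11 at 3. At 0.05/16, the strictest Benjamini-Hochberg step if the 16 items formed one family, power at odds ratio 2 is 12-15% for chi-square and 29-33% for van Elteren (90 per arm).

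**The case against.** The strongest reply is that this is a choice between two valid tests. The multinomial models in section 14.3 are built for outcomes measured at four visits, whereas overall tolerance and the questionnaires are recorded once, without a baseline, so a different method for them is not an inconsistency. The proportional-odds shift is assumed and favours a rank test. If the true shift is small, the odds ratio 1.25 row applies: about 4 points, with neither test useful. In polarised patterns the rank test loses far more than it gains under a shift. The two questionnaires share one scale and one analysis sentence, and section 7.2 uses the same verb for both, so splitting them is debatable. No other model in section 14.3 includes centre.

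Much of this stands and sets the weight: the test is valid, the figures are illustrations, and the issue is minor. It does not remove the point. The repeated-measures model need not carry over for the ordering to be used, since a simple rank test suits a single visit. The stated aim is improvement, which is a shift, and the category percentages would still show polarisation. Treating the efficacy items differently rests on the directional aim in section 6, which is thinner support than section 7.2 gives for tolerance. Stratifying follows the randomisation within centre and costs at most 0.2 points when the centres do not differ.

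The wording also does not exclude an ordered (Mantel-Haenszel) chi-square. If that was intended, saying so would settle the matter.

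**Conclusion.** The point holds, as a minor one. On the plain reading, overall tolerance is compared by a test that discards the ordering while the objective it supports is directional. Under a proportional-odds shift with 90 to 100 per arm, the cost relative to a centre-stratified rank test is about 17-18 points of power at odds ratio 2 and about 4 at 1.25, unadjusted. These figures rest on assumed category rates and on the shift being consistent across levels; for polarised differences chi-square is the better test. The 16 efficacy items lose somewhat more per item but matter less. This is lost efficiency, not bias or an inflated error rate, and it affects secondary outcomes only.

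**What to change.** State in the SAP, before unblinding:

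> Overall tolerance (dermatologist and subject ratings separately) and each of the 16 efficacy-questionnaire items will be compared between products by the Wilcoxon rank-sum test stratified by centre (van Elteren test), reported with the category percentages by product and the Mann-Whitney probability (ties counted as half, centre estimates combined with the van Elteren weights) with its 95% CI.

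The 12 acceptability items can stay on the chi-square test, since their objective is only to evaluate. If an ordered chi-square was meant from the start, naming it is the minimum change.

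For scale, an odds ratio of 2 corresponds to a Mann-Whitney probability of 0.58-0.60. In simulation at 90 per arm, the interval from the within-centre U-statistic variance covered 94.3-95.2%.

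The cost is wording only: no new data and no change to the primary analysis or sample size. Section 14 already has the SAP validated before database lock. The downside is low power for polarised differences, which would then be visible only descriptively in the category percentages.

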15. REPORT

A study report will be prepared in English by [SYLIA-STAT LANCRENON](#).

16. REGULATORY STATUS, ETHICS AND ADMINISTRATION

16.1. Regulatory status

According to French "Décret n°2017-884", the regulatory status of this study has been confirmed by the Sponsor as an "interventional study with minimal risks and constraints" (RIPH 2 mentioned to the 2° Article of the French Low L.1121-1) and has been submitted to Ethic Committee (CPP [SUD-OUEST ET OUTRE-MER II](#)).

16.2. Ethical conduct of the study

The study will be conducted in compliance with the protocol and all amendments to the protocol.

The protocol and all corresponding amendments affecting the design, rationale or objectives of the study, or the burden of or health risks for the subjects will only be implemented after having received written approval of the Ethic Committee (CPP).

The study will be conducted in accordance with:

- The World Medical Association - Declaration of Helsinki, (see Appendix 1)
- Local regulations.

16.3. General Data Protection Regulation

According to the General Data Protection Regulation (GDPR), data recorded during the study will be kept confidential and processed electronically, unless the subject objects, by the study centres and/or the sponsor

on its behalf in order to carry out a statistical analysis of the results obtained from the entire study population.

The Sponsor will also comply with the “Méthodologie de Référence MR001”.

16.4. Insurance

The Sponsor hold liability insurance in line with local regulatory requirements.

16.6. Protocol amendment

Any protocol amendment (change of the protocol) should be approved by the Sponsor and the investigator before implementation.

Any substantial modification will only be implemented after having received written approval of the Ethic Committee (CPP).

16.7. Subject information and informed consent process

All subjects and all legal representatives (for minor subjects) will receive verbal and written information concerning the study in accordance with the applicable local regulations, guidelines and the current SOP of each study centre. This information will explain the nature, purpose and risks of the study and will emphasise that participation in the study is voluntary and that the subject may withdraw from the study at any time and for any reason. All subjects and all legal representatives (for minor subjects) will be given opportunity to ask questions about the study and will be given sufficient time to consider their participation before consenting.

The subject’s and all legal representatives (for minor subjects) written informed consent to participate in the study will be obtained prior to any study related procedure being carried out.

The subject information sheet and informed consent must be written in a language that is understandable to the subject. The consent form should be signed and personally dated by the subject and/or all legal representatives (for minor subjects) and the investigator who conducted the informed consent discussion.

Two copies will be signed, one to be kept by the subject and one to be retained in the TMF.

16.8. Case report form / Source documents

The CRF and questionnaire will be written by Intertek and printed in duplicate.

The investigator will be responsible for the timely recording, completeness and accuracy of the information in the CRF.

Documents in which study data are first recorded/captured constitute Source Documents (see definition in Section 1, List of Abbreviations and Definitions of Terms).

In this study, the following documents will be considered as source documents for the following data:

1. Informed consent
2. Subject file: medical history, date of birth, sex, demographics (for CHU Nantes).
3. CRF: visit dates, physical examination, counting of the lesions, clinical assessments, corneometry, sebumetry and pH measurements, concomitant medication and adverse events,
4. Questionnaire
5. Laboratory results: confocal microscopy analysis, microbiome analysis.

The duplicate will be sent to SYLIA-STAT after monitoring for data entry.

16.9. Premature termination of the study

The study may be prematurely suspended or terminated by the Sponsor or the study centres. In case of premature suspension or termination, the study centres will promptly inform all study subjects and will provide appropriate follow-up.

If the clinical study is terminated for any reason, the sponsor should provide a written statement as to why the premature termination has taken place and notify the Ethics Committee and the Regulatory Authority as applicable.

If the study is prematurely suspended or terminated by the study centres without the prior agreement of the Sponsor, the study centres will inform the Sponsor as soon as possible and will provide the Sponsor with a detailed written explanation of the termination or suspension.

17. CONTROL OF THE DATA (MONITORING)

The initiation, monitoring and close down visits will be performed by the Sponsor.

The investigator makes a commitment to permit trial-related monitoring, audits, ethical review and regulatory inspections and provide direct access to source data/documents.

The Sponsor is responsible for establishing the schedule and procedures to be followed for monitoring this study. On-site visits will be made prior to study initiation and at regular intervals during the study. Communications by telephone, fax or email may be used as needed to supplement site visits. Prior to the beginning of this study, the investigator will be informed as to the anticipated frequency of the monitoring visits. In addition, the investigator will receive reasonable notification prior to each monitoring visit during the course of the study.

The purpose of these visits is to verify:

- adherence to the protocol;
- and the completeness and accuracy of the case report forms, and study related source document.

At each visit, the investigator will be expected to cooperate with Sponsor representative(s) for the review and verification of all case report forms, the product supply and inventory records and any additional records as may have been previously arranged.

18. QUALITY CONTROL

Each study centre will implement quality control procedures during the study to assure the data generated are accurate and the study was conducted correctly.

19. QUALITY ASSURANCE / INSPECTION

The Quality Assurance (QA) of Intertek may conduct audits during the study which may include review of protocol, amendments and study report and inspections of study conduct. In this case, an audit certificate will be produced. A copy of this document will be available in the study file and will be appended to the study report.

Representatives of the Sponsor and/or CA may also conduct audits and/or inspections of the testing facilities and/or the raw data and will have direct access to records of study participants held by each study centre. To facilitate such audits/inspections, appointments for visits will be requested by the Sponsor and/or CA in advance.

